The significance levels to be used for the analyses associated with these two comparisons will protect the overall study type I error probability to be one-sided 0.025 or less. The possibility of delayed vaccine effect is taken into account in computing the required number of deaths, (as modeled from the randomized Phase 2 trial). The projected trial size is 400 subjects per arm (approximately 1,200 subjects) with at least 85% power, and the final analyses will be event-driven and take place when 534 deaths have been realized for the comparisons involving all subjects randomized (Arm V+G versus Arm P, and separately Arm V versus Arm P).

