9.5 Trial Size

The Arm P reference data for planning this trial is specified as a median survival of 22 months based on the placebo arm of Dendreon D9902B. Based on exponential assumptions the corresponding hazard rate is 0.3781 and the corresponding three-year survival is 32.2%.

The hazard ratio to be used in the specific alternative hypotheses used to compute trial size is specified to be 0.68 for the main comparisons, that is, a 32% smaller hazard rate in Arm V+G or Arm V as compared to Arm P. This hazard ratio is based on hazard ratio estimates from the previously completed randomized Phase 2 trial with an allowance that the Phase 2 trial likely provides an over-optimistic estimate of the true hazard ratio. The hazard ratio estimate from the Phase 2 trial was 0.56, and was approximately 0.5 when delayed effect is taken into account (depending on the characterization of the delayed effect).

Simulations project that 534 events for each between-arm comparison are required for a minimum of 85% power to detect a 32% lower hazard rate. These calculations have taken in to consideration a delayed treatment effect (as found in the randomized phase 2 study). If there is less delayed effect the power will be greater. The projection for the time to realize the required number of deaths for final analysis is 4.6 years following the start of accrual.

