4.1.5. Number of Subjects and Required Number of Deaths

The number of subjects per arm is set to be 400 (Approximately 1200 total subjects). The accrual rate distribution is 19 months of linear ramp up followed by 11 months of constant rate of accrual (2.5 years to accrue approximately 1200 subjects). Note: The accrual distribution assumptions have been updated from the assumptions used originally to plan this trial and are based on current accrual experience. The table below has been revised to reflect these new accrual assumptions and there is no material modification to power, hypothesized hazard ratio, or any other important aspect of the trial design. As expected, the revised computations do change the projections for time to analysis. The assumptions used in [Table 1](#) match the assumptions used in the interim analysis planning computations outlined on pages 23 and 24. Please see [Appendix B](#) for more detail around the 19 month linear ramp followed by 11 months constant rate of accrual.

The trial is planned as an event driven trial. Simulation is used to compute the required number of deaths after setting other specifications. [Appendix A](#) to this document describes the simulation methodology. [Table 1](#) below shows the results of the simulations.

Table 1: Simulation Results

Case #	Delayed Effect	Specified # deaths	Time to specified deaths (y)	1-sided type I error probability estimate (%)	Power estimate (%)	Critical hazard ratio
1	No	340	3.4	1.17	90.2	0.784
2	Yes	340	3.3	1.13	44.5	0.784
3	Yes	534	5.1	1.23	86.1	0.823
4	No	534	5.2	1.12	98.8	0.823

Notes:

- Simulations are for the comparison of one of the experimental arms to control arm, that is, 800 subjects, 400 per arm, accrued over two years, with a 19 month ramp time followed by a constant accrual rate for 11 months (2.5 year total accrual).
- 10,000 replications for each case.
- Significance level is one-sided 0.0125. The column “One-sided type I error probability estimate (%)” from the simulations should be approximately 1.25%. Target power with delayed effect is 85% or more.
- The control arm data are generated under the exponential distribution with 22 month median survival.
- The experimental arm data under the specific alternative and when delayed effect (if applicable) are generated so that hazard rates are equal for 4 months (hazard ratio = 1), followed by a linear transition over next 4 months to target hazard ratio of 0.68, with hazard ratio = 0.68 from 8 months onward.

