- The estimated type I error and power are the percent rejection of the null hypothesis when the data are simulated under the null or specific alternative hypotheses, respectively. The estimated type I error probabilities in the table are sufficiently close to 1.25% considering they are estimated from simulations.
- The “Critical hazard ratio” is the maximum hazard ratio that resulted in rejection of the null. This is an estimate of the threshold of significance. At the end of the trial larger hazard ratios will not result in rejection of the null hypothesis.

Case # 1 simulates a trial without delayed effect and a target power of 90% or greater and corresponds to conventional (proportional hazards) trial sizing computations, where the usual formula computed a requirement for 340 deaths. Case # 2 is based on the required number of deaths computed for Case # 1 (340) but with the data in the simulations generated under the specified delayed effect. The power for an analysis at 340 deaths when the specified delayed effect is applicable is not sufficient (44.5%). Note that 340 deaths are realized sooner than for Case # 2 than Case # 1 because the experimental arm will have a higher early hazard rate in Case # 2 than in Case # 1.

Case # 3 represents a solution to the required number of deaths for a target power of 85% or more under the delayed effect specified. The number of deaths required is found to be 534, with time to realization of 534 deaths projected to be 5.1 years. Case # 4 illustrates the estimated power of a trial with 534 deaths at the final analysis but without delayed effect. The high power (98.8) is the result of early events being differentiating.

Thus, these simulations show that a final analysis at 534 deaths provides protection against unacceptable loss of power if the projected delayed effect is applicable, and yet assures that the type I error probability is protected. The trial's power will be 85% or greater if the delayed effect does not exceed that specified in the simulations.

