9.7. Immune Monitoring

Immune Monitoring data will be presented in the data listings.

10. Quality of Life

Subject-reported quality-of-life (QOL) data will be presented in the data listings.

11. Radiology

Radiological assessments will be performed at Screening, Week 13, Week 25 EOT, and at the 6-month long term follow-up visit.

Radiology data will be presented in the data listings.

12. Interim Analysis

This section describes the interim analysis plan (IAP) to be executed by the independent statistician and assessed by the DMC. The specific IAP results are closed to the sponsor unless one of the criteria are met, and even then the DMC will use its discretion regarding the communications of results to the sponsor, with patient safety balanced against benefit being the primary concern. This IAP consists of the ability to detect early evidence of efficacy and also futility.

The statistical computations used to devise this IAP take into account the possibility of a delayed effect of the same magnitude as used to plan the trial size but the statistical tests will ignore the possibility of delayed effect because there cannot be certainty that a delayed effect exists. Stated another way, the statistical tests to be done as specified in the IAP are optimal in cases where the hazard ratio is proportional; the alternative is intractable because it would be to use parametric statistics in a situation where the underlying form of the failure-time distribution is not known. Thus, if the possibility of a delayed effect were not taken into account and it actually exists then the IAP would have lower power to detect early efficacy than anticipated because early events would not be discriminatory for efficacy, and a conclusion of futility would have increased power because early events would be give a false signal about lack of efficacy. By contrast, if the possibility of delayed effect were taken into account when a delayed effect does not exist then the IAP will have greater power than anticipated to detect early efficacy whereas futility would have diminished power than anticipated.

The IAP is designed so that interim analyses for a comparison are to be executed at 40%, 60%, and 80% information times, corresponding to 214, 321, and 427 deaths, with the final analysis at 534 deaths as previously discussed.

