The one-sided significance criteria to be used for early detection of efficacy analyses are 0.000135, 0.00147, 0.00501, respectively, with the adjusted final analysis to use 0.01063. These significance levels were computed using SAS PROC SEQDESIGN as one-sided O'Brien-Fleming boundaries with an overall one-sided type I error probability of 0.0125. Following is the SAS code used to compute these intervals.

```
proc seqdesign boundaryscale=pvalue;  
  design  
    nstages=4  
    info=cum(0.4 0.6 0.8 1)  
    method=obf  
    alt=upper  
    stop=reject  
    alpha=0.0125  
  ;  
run;
```

The early detection of efficacy is to use the same statistical testing methodology as specified for the primary analysis. The statistical characteristics for the interim analysis event-driven time-points and significance levels are computed using simulations. The simulation methodology for delayed effect is described in [Appendix A](#). The following table shows the statistical operating characteristics of this plan based on 10,000 simulation replicates. For example, when the alternative hypothesis is true (average hazard ratio = 0.68) then at the second interim analysis is projected for 3.2 years following the start of randomization and the estimated cumulative probability of rejecting the null hypothesis is 0.1571 (with confidence interval as shown). Also shown is the largest hazard ratio found for which the null hypothesis was rejected (rej HR), showing that at this interim analysis a hazard ratio less than or equal to 0.716 will pass the criterion for early efficacy (an estimate of the critical hazard ratio). Please note that these simulations are consistent with the targeted overall one-sided type I error of 0.0125: for analysis 4 (“#” column) the proportion of trials rejected (“rejected” column) under the null hypothesis (row with “null” in the “hyp” column) is 0.0127, and is close enough to 0.0125 considering computations were done using simulation.

Statistical Operating Characteristics of the Interim Analysis Plan

Simulation estimates (cumulative, # replications = 10000):

#	events	hyp	time	test	rejected	95% CI	rej HR		
1	214	null	2.5	futile	0.0771	0.0719 to 0.0825	≥ 1.212		
				superior	0.0000	0.0000 to 0.0004	≤ 0.000		
		alt	2.5	futile	0.0054	0.0041 to 0.0070	≥ 1.216		
				superior	0.0065	0.0050 to 0.0083	≤ 0.603		
				null	3.0	futile	0.2297	0.2215 to 0.2381	≥ 1.090
						superior	0.0013	0.0007 to 0.0022	≤ 0.712

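### The promised minimum of 85% power belongs to a single-look test; with the planned interim analyses the SAP's own table gives 83.9%, and the protocol's 4.6-year readout matches only the SAP's null rows

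*SAP*

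**What the plan says.** Three places give a power floor.

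- Protocol synopsis, Statistical Methods: 400 subjects per arm "with at least 85% power, and the final analyses will be event-driven".
- Protocol 9.5: "Simulations project that 534 events for each between-arm comparison are required for a minimum of 85% power to detect a 32% lower hazard rate".
- SAP 4.1.5: "power will be 85% or greater if the delayed effect does not exceed that specified in the simulations".

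The source is SAP Table 1, Case 3: delayed effect, 534 deaths, power 86.1%, critical hazard ratio 0.823. The notes to that table say "Significance level is one-sided 0.0125", with no adjustment for interim looks.

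SAP section 12 and protocol 9.8 describe the design that will be run. Looks are planned at 40%, 60% and 80% information, "corresponding to 214, 321, and 427 deaths, with the final analysis at 534 deaths as previously discussed". The one-sided efficacy levels are "0.000135, 0.00147, 0.00501, respectively, with the adjusted final analysis to use 0.01063". A futility test at 0.00001 is made at each interim. The section 12 table for this plan, under the delayed effect, shows cumulative rejection of 0.8388 at the fourth analysis.

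On timing, protocol 9.5 says: "The projection for the time to realize the required number of deaths for final analysis is 4.6 years following the start of accrual". SAP Table 1 gives 5.1 years for Case 3. The section 12 table gives 5.0 years under the delayed alternative and 4.6 years under the null.

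**The concern.** The power floor is taken from a test the trial will not perform. O'Brien-Fleming looks at 40%, 60% and 80% lower the final significance level, so power at a fixed number of deaths must fall. Case 3 sits only 1.1 points above the target, and 534 was chosen as the number of deaths that meets it. Any loss of more than 1.1 points breaks the promise.

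The timeline has a similar problem. The date that matters for planning is the one that applies if the vaccine works as assumed, because fewer deaths per year then occur in the experimental arm. The figure in protocol 9.5 agrees with the SAP's no-effect scenario instead. The DMC, investigators and regulators would be relying on a power floor and a readout date that the SAP contradicts.

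**Working it through.** **Inputs.** Control arm exponential with median 22 months. Hazard ratio 1 to month 4, linear to 0.68 at month 8, then 0.68 (SAP 4.1.3). 400 per arm; accrual over 30 months, with a 19-month linear ramp then 11 months constant (SAP 4.1.5, Appendix B). Looks and levels from SAP section 12. SAP 4.1.5 states that Table 1 and the interim computations share the same assumptions, so the two tables can be compared directly.

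**1. Model set-up.** Control hazard = ln 2 / (22/12) = 0.3781 per year; three-year survival = exp(−3 × 0.3781) = 32.2%. Both match the SAP. Experimental survival times come from the integrated hazard in SAP Appendix A with d = r = 4 months: beyond month 8, H₂(t) = (λ₁ − λ₂)(d + r/2) + λ₂t, with λ₂ = 0.68 λ₁. The test is an unstratified logrank test.

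**2. Reproducing Table 1** (single look at 0.0125; 60,000 replicates for the delayed cases, 6,000 for the others).

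| Case | Deaths | Delay | SAP power | Recomputed |
|---|---|---|---|---|
| 1 | 340 | no | 90.2% | 90.0% |
| 2 | 340 | yes | 44.5% | 44.4% |
| 3 | 534 | yes | 86.1% | 85.0% |
| 4 | 534 | no | 98.8% | 98.8% |

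For Case 3, shorter runs gave 85.4% to 85.6%. The single-look design therefore clears 85% with little to spare. As a formula check on Case 1, Φ(√340/2 × |ln 0.68| − 2.241) = Φ(1.314) = 90.6%.

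**3. The significance levels.** Multivariate normal integration of the four stated levels gives an overall one-sided error of 0.01250, so the boundaries are correct. Using 0.0125 at the final look after the same interims would give 0.0141 per comparison. Single-look power therefore cannot be kept by leaving the final level unadjusted.

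The critical hazard ratio at 534 deaths is exp(−2z/√534):
- at 0.0125, z = 2.241, giving 0.824 (Table 1: 0.823);
- at 0.01063, z = 2.303, giving 0.819 (section 12, null row: 0.819).

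**4. Power of the design as planned** (delayed alternative, cumulative efficacy).

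| Deaths | 214 | 321 | 427 | 534 |
|---|---|---|---|---|
| SAP section 12 | 0.0065 | 0.1571 | 0.5417 | 0.8388 |
| Recomputed, efficacy bounds only | 0.0080 | 0.1589 | 0.5430 | 0.8367 |

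Adding the futility stop gives 0.8360, a loss of under 0.1 point. Shorter runs gave 84.0% to 84.3%.

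For the SAP figure with 10,000 replicates, the standard error is √(0.8388 × 0.1612 / 10,000) = 0.0037. The 95% interval is 0.8388 ± 1.96 × 0.0037, or 83.2% to 84.6%. Tested against 85%, z = −0.0112 / √(0.85 × 0.15 / 10,000) = −3.1, so simulation noise does not explain the gap.

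Shortfall: 85.0 − 83.9 = 1.1 points against the promise, and 86.1 − 83.9 = 2.2 points against Table 1.

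**5. Timing** (mean years from start of accrual).

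| Deaths | 214 | 321 | 427 | 534 |
|---|---|---|---|---|
| Null, SAP | 2.5 | 3.0 | 3.7 | 4.6 |
| Null, recomputed | 2.47 | 3.00 | 3.66 | 4.56 |
| Delayed alternative, SAP | 2.5 | 3.2 | 4.0 | 5.0 |
| Delayed alternative, recomputed | 2.54 | 3.16 | 3.96 | 5.05 |

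The SAP's no-delay alternative takes 5.2 years in Table 1 and 5.1 in section 12. No alternative row gives 4.6. The gap is 0.4 to 0.5 years, or about five to six months.

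**The case against.** The strongest reply is that the shortfall is small and not hidden. Section 12 prints 0.8388 with its interval and describes the target as approximately 85%; SAP 4.4 says interim analysis was added to the plan. The single-look test used to choose 534 does reach 85%. All this is true, and it limits the weight of the point. But an approximate target in a table note does not support a stated minimum elsewhere, and SAP 4.1.4 sets the target itself at 85% or more.

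Second, success is defined as either comparison succeeding. If both arms have the planned effect, a simulation with a shared control arm (6,000 replicates) puts the chance of at least one success at 94.5%. This weakens the point for the synopsis, which does not say whether its 85% is per comparison. It does not help protocol 9.5, which attaches the figure to each comparison.

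Third, 4.6 years may be left over from an earlier accrual plan rather than read from the wrong row. SAP 4.1.5 says the accrual assumptions were revised and that time projections changed, and a Table 1 note still mentions two-year accrual. Assuming 24 months' accrual with a 6- to 9-month ramp (the documents do not give the original ramp), the delayed alternative reaches 534 deaths at 4.58 to 4.63 years. The origin cannot be settled from the documents. Either way, protocol 9.5 disagrees with the current SAP. Because the analysis is event-driven, the projection affects planning and not the test.

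**Conclusion.** The concern holds. Under the planned delayed effect and with the planned interim analyses, power at 534 deaths is about 84% per comparison (SAP 83.9%; recomputed 83.6% to 84.3%), not a minimum of 85%. Nearly all the loss comes from the sequential efficacy testing; the futility rule contributes almost nothing. Under the SAP's current accrual, 4.6 years is the time to 534 deaths only if there is no treatment effect; under the delayed effect it is 5.0 to 5.1 years.

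This is a misstated guarantee and a wrong projected date, not a seriously underpowered trial. The result rests on the SAP's own assumptions: exponential control survival with a 22-month median, the stated delay, the stated accrual, and no loss to follow-up. Loss to follow-up would mainly lengthen the time to 534 deaths. So would the section 12 rule that each analysis waits until both comparisons reach their count.

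**What to change.** **Restate the figures.** In the protocol synopsis, protocol 9.5 and SAP 4.1.4 to 4.1.5, give power as about 84% per comparison with the interim plan, and time to final analysis as about 5.0 to 5.1 years under the planned effect. Label Table 1 as single-look, and give 0.819 as the critical hazard ratio at the final analysis. Align the 0.0125 criterion in SAP 8.2.2 with the final level of 0.01063 in section 12. This costs wording only.

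**Optional: restore 85%.** Simulation gives 85.2% at 545 deaths (looks at 218, 327 and 436) and about 86% at 550. A constant-drift formula based on the SAP's 0.8388 gives a cautious 549: 534 × [(2.303 + 1.036) / (2.303 + 0.990)]² ≈ 549. No extra patients are needed. Mean time rises from 5.05 to 5.19 years at 545 and 5.26 at 550, a delay of about two months.

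The delay is not the whole cost. The look counts in protocol 9.8 and SAP section 12 would change, and so would the end of follow-up, which is set 12 months after the required deaths. If a look has already taken place, boundaries must be recomputed for the actual information fractions. The decision would have to be made blind to interim results. For about one point of power, restating the figures is the proportionate minimum.

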4.2. Randomization, Stratification, and Blinding

Block randomization will be used to randomly assign subjects in a 1:1:1 manner. Randomization will be stratified according to the following two factors, PSA (equal and above or below 50 ng/ml) and LDH (equal and above or below 200 U/L). These two stratification factors will be used to create a four-level categorical stratification variable for the following combinations of the stratification factors: (PSA < 50 & LDH < 200), (PSA < 50 & LDH ≥ 200), (PSA ≥ 50 & LDH < 200), and (PSA ≥ 50 & LDH ≥ 200). This stratification variable will be used to stratify analyses as specified subsequently.

Unblinding will be performed only in the event of a medical emergency in which the Investigator determines that knowledge of the subject's treatment assignment is necessary for effective treatment. If unblinding is required, the Investigator must contact the Medical Monitor or designee who will record who requested the unblinding, for what purpose, and for which subject, and will notify the DMC in a timely manner.

4.3. Analysis Sets

Three analysis sets are defined for this trial. The Intent-to-Treat set (ITT) includes all subjects who are randomized. The full analysis set (FAS) includes all subjects initiating study intervention. The Safety analysis set includes all subjects initiating study intervention. The FAS and safety analysis set are the same.

All efficacy analyses will be performed on the ITT set and the FAS. Subjects will be analyzed and summarized based on the arm into which they were randomized. Efficacy analysis performed on the ITT analysis set will be considered to be the primary indicator of efficacy. Analysis performed on the FAS will be considered to be supportive.

All safety analyses will be performed on the Safety set and subjects will be analyzed and summarized based on the treatment they actually received.

4.4. Changes in Planned Analysis

The analysis as described in the protocol has been expanded to include the analysis of tumor regression and growth rates. Interim analysis has been added.

5. Subject Disposition

Subject enrollment will be summarized for each site by treatment arm and overall for the FAS.

Subject disposition will be summarized by treatment arm and overall for the FAS. Percentages for this table will be based on the total number of subjects in each treatment arm and overall.

The reasons for study treatment discontinuation will be summarized by treatment arm and overall. The reasons for study treatment discontinuation are listed on the treatment completion eCRFs.

6. Demographics and Baseline Characteristics

6.1. Demographics

A summary of demographics and baseline characteristics will be presented by treatment arm and overall for the FAS. The demographic characteristics consist of age, age category, sex, ethnicity, race, and prior smallpox vaccination status. Baseline height and weight will also be presented using descriptive statistics.

For subjects who provide date of birth, age will be calculated as the integer part of $(\text{Date of Informed Consent} - \text{Date of Birth} + 1)/365.25$. Age will also be categorized using the categories 18-<25, 25-<45, 45-<65, and 65 or over, and will be presented using frequencies and percentages. The number and percentage of subjects' ethnicity (Hispanic or Latino, Not Hispanic or Latino, or Not Reported) as well as reported race categories will also be reported. Reported race categories include White, Black, Asian, American Indian or Alaska Native, Native Hawaiian or Other Pacific Islander, and Multiracial.

All demographic and baseline characteristic data will be listed for each subject.

